2.2 Primary Objectives

- 2.2.1 To determine if it is feasible to administer a regimen of cisplatin/RT in HIV-infected women with LACC on ART. This regimen is considered standard therapy for women with LACC who are not HIV infected. Feasibility will be assessed based on:
 - 2.2.1.1 Treatment completion proportion – the proportion of participants who complete the cisplatin/RT regimen
 - 2.2.1.2 Screening ratio: the number of potential participants screened per enrolled participant
 - 2.2.1.3 Availability proportion: follow-up completion proportion at 6 and 12 months

2.2.2 To evaluate the safety and tolerability of concomitant chemoradiotherapy with cisplatin in HIV-infected women with LACC who are also receiving concomitant ART.

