3.3 Number of Participants to be Enrolled

This study will enroll 45 participants, of whom we anticipate 38 will be evaluable. Once all sites are open for accrual, we anticipate the accrual rate to be 4-6 per month. Accrual is expected to take an estimated 24 months. All participants will have a minimum of 12 months of follow-up. We anticipate that at least 50% of recruited participants will be Stage 3 and 4A.

Accrual Targets					
Ethnic Category	Sex/Gender				
	Female		Male		Total
Hispanic or Latino	0	+	0	=	0
Not Hispanic or Latino	45	+	0	=	45
Ethnic Category: Total of all subjects	45 (A1)	+	0 (B1)	=	45 (C1)
Racial Category					
American Indian or Alaskan Native	0	+	0	=	0
Asian	0	+	0	=	0
Black or African American	45	+	0	=	45
Native Hawaiian or other Pacific Islander	0	+	0	=	0
White	0	+	0	=	0
Racial Category: Total of all subjects	45 (A2)	+	0 (B2)	=	45 (C2)
	(A1 = A2)		(B1 = B2)		(C1 = C2)

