3.5.2 Enrollment

After the screening evaluations are completed and the participant is determined to be eligible the participating site will complete the protocol-specific eligibility checklist and enroll the participant into AMC-081 Treatment Segment (Segment B) on-line via the AMC AdvantageEDCSM Internet Data Entry System. The

participating site will ensure the participant meets all eligibility criteria prior to completing the protocol-specific eligibility checklist. Participants will be enrolled on-line via the AMC Internet Data Entry System no more than 1 week prior to the initiation of treatment (enrollment 1 day prior to or on the day of treatment is strongly encouraged). Once the eligibility checklist is submitted, a system-generated confirmation will be sent to the site staff, AMC ODMC, and Protocol Chair upon successful registration.

If the on-line system is inaccessible for Registration (Treatment Segment), the site should notify the AMC ODMC via email at [contact] or via phone at [name] for further instructions. If the AMC ODMC cannot be reached, please follow the manual randomization procedures detailed in the AMC-081 Manual of Procedures.

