11.0 STATISTICAL CONSIDERATIONS

11.1 Statistical Analysis Plan

Treatment completion rate will be estimated as proportion of all women who complete cisplatin of those who initiate cisplatin treatment. The binomial proportion and its 95% confidence interval will be used to estimate the treatment completion rate.

The screening ratio will be estimated as the number of patients screened divided by the number of patients enrolled on the study. The Poisson rate and its 95% confidence interval will be used to estimate the screening ratio.

The Kaplan-Meier method will be used to describe the progression-free survival (PFS) and overall survival (OS). We will generate KM curves for Stage I/II participants as well as Stage III/IV participants. The stratified log-rank test will be used to evaluate the association of HAART use, node positivity including enlarged pelvic nodes, stratified for stage. Those factors that are significantly associated with PFS and OS will be incorporated into a proportional hazards model. The one-year PFS and OS will be estimated using the cumulative proportion progression free (for PFS) or surviving (for OS) and its 95% confidence interval.

Frequency tables will be used to summarize the occurrences of adverse events by severity grade. Frequencies of specific adverse events will be tabulated.

Toxicity assessment: All toxicities will be reported on standard case report forms at visits and graded by NCI CTC v4.0. There will be standard dose reduction schedules. All dose delays, dose reductions, and missing doses will be tracked via CRFs during therapy. These will be tabulated and reported as rates.

Adherence assessments are planned weekly during cisplatin therapy and at the end of protocol therapy. Participants will be considered inadherent to ARV if they report missing doses on more than one adherence assessment. The proportion of participants who were inadherent to ARV during protocol therapy will be estimated using the binomial proportion and its exact 95% confidence interval.

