11.2 Sample Size Considerations

The primary outcome measure for this trial is treatment completion rate. A treatment completion rate of 70% or above would be sufficient to consider this regimen for further study. To test the null hypothesis that the treatment completion rate is 0.50 against the alternative that it is 0.70 at the one-sided 0.0510 level with 0.90 power will require 38 evaluable patients. To allow for potential 15% dropout, 45 patients will be enrolled in the study.

We will recruit 45 participants from the AMC core sites in Africa over an estimated 2 year period of time and have a minimum of 1 year of follow-up. We anticipate that at least 50% of recruited participants will be Stage 3 and 4. This will be helpful in stratified analyses by stage and node positivity.

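### The Poisson interval planned for the screening ratio is the wrong model: it is too narrow when the ratio is above 2 and too wide, with impossible limits, when the ratio is near 1

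*Combined protocol and SAP*

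**What the plan says.** Section 2.2 lists three measures of feasibility under the first primary objective. The second is "Screening ratio: the number of potential participants screened per enrolled participant". Section 9.1.2 repeats it as an outcome measure.

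Section 11.1 gives the estimator, "The screening ratio will be estimated as the number of patients screened divided by the number of patients enrolled on the study", and then the interval, "The Poisson rate and its 95% confidence interval will be used to estimate the screening ratio".

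Two other places fix the structure of the data. Section 3.3 sets the denominator: "This study will enroll 45 participants, of whom we anticipate 38 will be evaluable". Sections 3.5.1 and 3.5.2 set the order of events. A woman is registered for screening after consent, and enrolment comes later: "After the screening evaluations are completed and the participant is determined to be eligible the participating site will complete the protocol-specific eligibility checklist". Enrolled women are therefore a subset of screened women.

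No section states an expected ratio, a target, a required precision or a decision rule for this measure.

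**The concern.** A Poisson rate suits a count of events over an exposure that is separate from the count. Here the denominator is contained in the numerator. Each screened woman either enrols or does not, so the ratio is a binomial proportion turned upside down. The Poisson model ignores this. It allows fewer women screened than enrolled, which cannot happen, and its variance has the wrong form.

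Item 7 of the summary in section 1.0 says the trial will supply screening rates for planning a phase II trial. The ratio is there to be estimated, so its interval is the main statement about how well it is known. If screening is inefficient, the interval will make the ratio look more certain than it is, and a screening workload for the next trial could be planned on limits that are too tight.

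**Working it through.** **Inputs.** Enrolled E = 45 (sections 3.3 and 11.2). Nominal level 95% (section 11.1). The true ratio R is not stated in the documents, so it is varied from 1.25 to 10. Assumptions: screening continues until 45 are enrolled, and each screened woman enrols independently with the same probability p = 1/R.

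**Variance.** Under these assumptions the number screened, S, is negative binomial:

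- mean of S = E/p = 45R
- variance of S = E(1 − p)/p² = 45R(R − 1)
- variance assumed by the Poisson model = 45R

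The ratio of true to assumed variance is R − 1. It is 1 at R = 2, 3 at R = 4 and 0.25 at R = 1.25. To a large-sample approximation, the coverage of a nominal 95% Poisson interval is 2Φ(1.96/√(R − 1)) − 1. At R = 4 this is 2Φ(1.96/1.732) − 1 = 74.2%. The number enrolled does not appear in the formula, so a larger trial would not cure the fault.

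**Exact coverage.** The exact Poisson limits for S are χ²(0.025; 2S)/2 and χ²(0.975; 2S + 2)/2, each divided by 45. The alternative is the Clopper-Pearson interval for 45/S with its limits inverted. Coverage is the sum of the negative binomial probabilities over every S whose interval contains R.

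| True R | Poisson coverage | Inverted Clopper-Pearson coverage | Chance that Poisson lower limit is below 1 |
|---|---|---|---|
| 1.25 | 100.0% | 96.5% | 81% |
| 1.5 | 99.5% | 96.2% | 7% |
| 2 | 95.7% | 96.0% | 0% |
| 2.5 | 90.4% | 96.1% | 0% |
| 3 | 84.1% | 96.1% | 0% |
| 4 | 75.6% | 95.8% | 0% |
| 5 | 68.4% | 95.8% | 0% |
| 6 | 63.2% | 95.9% | 0% |
| 10 | 49.1% | 95.8% | 0% |

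**Two worked results.**

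- 180 screened, 45 enrolled (ratio 4.00). Poisson: 154.66/45 to 208.30/45 = 3.44 to 4.63, width 1.19. Clopper-Pearson for 45/180 is 0.1886 to 0.3199, which inverts to 3.13 to 5.30, width 2.17. The Poisson interval has 1.19/2.17 = 55% of that width.
- 50 screened, 45 enrolled (ratio 1.11). Poisson: 37.11/45 to 65.92/45 = 0.82 to 1.46. Clopper-Pearson for 45/50 is 0.7819 to 0.9667, which inverts to 1.03 to 1.28.

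**Where the impossible limits begin.** At S = 59 the Poisson lower limit is 44.91/45 = 0.998. At S = 60 it is 45.79/45 = 1.017. The limit is therefore below 1 whenever 59 or fewer women are screened, which is a ratio up to about 1.31.

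**Sensitivity at R = 4.** The form of the Poisson interval and the stopping rule make little difference. Coverage is 74.3% with a Wald interval, 74.8% with a log-scale Wald interval, 76.0% with 38 in place of 45, 76.9% if the number screened is fixed instead, and 75.0% if accrual stops at a fixed time so that both counts are random.

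**The case against.** The strongest objection is that the size of the error depends on a ratio the documents never give. A ratio of 4 is an illustration. Between about 1.5 and 2.25 the Poisson interval does little harm: coverage is 99.5% at 1.5, 98.2% at 1.75 and 92.7% at 2.25, and limits below 1 are uncommon. Section 3.5.1 counts screening from after consent and refers to tests required before the screening segment, so some selection happens before the count starts and a modest ratio is possible. On the other hand, section 2.2 speaks of potential participants, which could be counted more widely. The two faults also cannot both affect one trial: under-coverage needs a ratio above 2, and impossible limits need one near 1.

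Second, no decision rests on this interval. Section 11.2 says: "The primary outcome measure for this trial is treatment completion rate". Only that measure has a threshold, a significance level and power. The estimate of the ratio is itself unaffected, and a reader given both counts could compute a better interval.

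Third, the binomial interval also rests on assumptions. Section 6.2.1 holds enrolment of women with low CD4 counts after the first three, and the sites are in different countries, so the enrolment probability may vary. In an illustrative simulation with assumed clusters of 15 screened women, at ratios 2 and 4, its coverage was about 92% to 94% at an intraclass correlation of 0.02 and 88% to 89% at 0.05.

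All of this stands as a limit on weight. None of it makes the Poisson model right. The plan states no ratio near 2 that would excuse it, nothing elsewhere in the documents corrects the sentence, and the binomial form remains the better model even with some clustering.

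**Conclusion.** The point holds. The Poisson interval is the wrong model for screened/enrolled, and its error is set by R − 1. Above a ratio of 2 it is too narrow, with coverage of 84.1% at 3, 75.6% at 4 and 49.1% at 10. Near 2 it is harmless. Below 2 it is too wide, and with 59 or fewer screened its lower limit is impossible. These figures assume 45 enrolled and independent screening outcomes with a constant enrolment probability. Which of them applies is unknown until the ratio is observed.

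The consequence is misstated precision on a primary feasibility measure meant for planning a later trial. The main test and the sample size are untouched. It should be corrected because the error is structural and the remedy costs almost nothing.

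**What to change.** Replace the interval sentence in section 11.1. Estimate the enrolment proportion as enrolled/screened with an exact binomial (Clopper-Pearson) 95% confidence interval, and report the screening ratio as its reciprocal with the limits inverted. Report both counts. The same section already plans an exact binomial interval for antiretroviral non-adherence, so no new method is brought in.

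Two additions would help. State which women count as screened (for example, all those registered in the screening segment), and show the counts by site so that any variation in the enrolment proportion can be seen.

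The cost is one or two sentences. Data collection, sample size and conduct do not change.

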2.3 Exploratory Objectives

2.3.1 To determine the 1-year progression-free survival (PFS) of HIV-infected women with locally-advanced invasive cervical cancer (LACC) Stage IB, II, III, and IVA who receive weekly cisplatin concomitant with radiotherapy and ART.

2.3.1.1 Determine PFS in all registered participants, regardless of completion (intent to treat-ITT)

2.3.1.2 Determine the PFS in the subset of participants who complete the prescribed chemotherapy/ radiotherapy

2.3.1.3 Compare PFS in these subjects with PFS of HIV-uninfected subjects as reported in the literature, stage for stage.

2.3.2 To describe the effects of treatment on participants' CD4 counts, HIV viral load and concurrent AIDS-defining conditions.

2.3.3 To describe cervical cancer recurrence patterns in HIV-infected participants with LACC defined as loco-regional and/or distant recurrences.

2.3.4 Determine 1-year overall survival and causes of death (i.e., cancer-related, HIV-related, or other).

2.3.5 To evaluate the effects of weekly cisplatin concomitant with radiotherapy on adherence to ART.

2.3.6 Collect serum and cervical and anal swab material for the following exploratory analyses:

2.3.6.1 To describe the distribution of HPV DNA types and HPV strain variants in cervical and anal swabs collected at baseline, prior to initiation of study treatment;

2.3.6.2 To assess the concordance between HPV DNA types and HPV strain variants detected in cervical and anal swabs collected at baseline, prior to initiation of study treatment;

2.3.6.3 To investigate the effect of study treatment on HPV persistence in cervical and anal swabs and its relationship to cervical cancer persistence or recurrence;

2.3.6.4 To describe the gene methylation profiles in cervical and anal swabs collected at baseline, prior to initiation of study treatment;

- 2.3.6.5 To investigate the relationship between baseline gene methylation profiles and cervical cancer persistence or recurrence;
- 2.3.6.6 To measure serum antibody titers to HPV 16 and HPV 18 at baseline and on study, and to determine whether baseline titers or changes during therapy correlate with cervical cancer persistence or recurrence.

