To determine the HPV DNA types and HPV strain variants present in cervical cancer and in the anus of cervical cancer patients, frequency tables of HPV DNA types and HPV strain variants will be constructed for cervical and anal samples at baseline, end of treatment and at recurrence (if applicable). The binomial proportion and its 95% confidence interval will be used to estimate the proportion of each HPV DNA type and each HPV strain variant that occurs in at least 5% of patients in cervical or anal specimens. Concordance between anal and cervical specimens with respect to detection of specific HPV DNA types and HPV strain variants will be assessed using McNemar's chi-square test.

Changes in HPV DNA types and strain variants between baseline and post-treatment measurements will be assessed using McNemar's chi-square test for each DNA type and

strain variant. Proportional hazards models and logistic regression models will be used to evaluate the association of change in DNA types with progression free survival and local control, respectively.

The binomial proportion and its 95% confidence interval will be used to estimate the proportion of patients who have abnormally methylated genes for each gene tested.

Gene methylation profiles will be summarized at baseline.

Concordance between gene methylation profiles between cervical and anal swabs will be assessed at baseline using the kappa statistic.

The chi-square test will be used to assess the association between baseline gene methylation profiles and cervical persistence or recurrence.

The logistic regression model will be used to assess the effects of HPV-16 and HPV-18 serologic titer levels with disease persistence or recurrence using the logarithmic transformation for the titer levels. Similarly, the effects of changes in HPV-16 and HPV-18 titer levels from baseline to treatment on outcome measures (progression free survival, local control) will be assessed using proportional hazards models and logistic regression models.

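### McNemar's test is the only method named for cervical-anal HPV concordance, but it compares prevalence between the sites and does not measure agreement

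*Combined protocol and SAP*

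**What the plan says.** Objective 2.3.6.2, repeated as item 6b of the Study Synopsis, is "To assess the concordance between HPV DNA types and HPV strain variants detected in cervical and anal swabs collected at baseline", before treatment starts. Section 11.1 names McNemar's chi-square test as the method for detection at the two sites, in the sentence that begins "Concordance between anal and cervical specimens with respect to detection of specific HPV DNA types and HPV strain variants will be assessed using".

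Three other statements in section 11.1 bear on this:

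- For methylation, measured on the same two kinds of swab at the same time point, the method is different: "Concordance between gene methylation profiles between cervical and anal swabs will be assessed at baseline using the kappa statistic".
- McNemar's test is also assigned to change over time: "Changes in HPV DNA types and strain variants between baseline and post-treatment measurements will be assessed using McNemar's chi-square test".
- The remaining descriptive HPV output, with recurrence as its last time point, is that "frequency tables of HPV DNA types and HPV strain variants will be constructed for cervical and anal samples at baseline, end of treatment and at" that event, plus a proportion with a 95% confidence interval for each type or variant found in at least 5% of patients. The plan does not say that these tables cross-classify the two sites within each woman.

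**The concern.** Concordance asks whether a woman who carries a given HPV type at the cervix also carries it at the anus. McNemar's test asks whether the type is equally common at the two sites. These are different questions. Two sites can have identical prevalence with no woman sharing the type, or agree in most women while one site is positive more often.

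The plan gives no rule for interpreting the test. A reader who takes its p-value as the answer to 2.3.6.2 could see concordance where there is none, or discordance where agreement is substantial. Section 1.2.1 says little is known about anal HPV in women with cervical cancer, so there is little outside evidence that would expose a misreading.

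**Working it through.** The documents give no sample size, power or significance level for this analysis, so there is no planned figure to reproduce. The check is how the test behaves on paired 2x2 tables.

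**Inputs.** Section 3.3 says: "This study will enroll 45 participants, of whom we anticipate 38 will be evaluable". I use n = 38 for illustration. Usable pairs may be fewer, because Appendix XI excludes specimens negative for beta-globin. The documents give no prevalences by site for this population, so every table below is an assumption.

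**Notation and formulas.** Let a = both sites positive, b = cervix only, c = anus only, d = neither.

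- McNemar chi-square = (b − c)² / (b + c). Neither a nor d enters.
- Overall agreement: po = (a + d) / n.
- Chance agreement: pe = [(a + b)(a + c) + (c + d)(b + d)] / n².
- Kappa = (po − pe) / (1 − pe).
- Positive agreement = 2a / (2a + b + c).

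**Table 1: no woman shares the type, (a, b, c, d) = (0, 10, 10, 18).**

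- McNemar = (10 − 10)² / 20 = 0; p = 1.0 (uncorrected and exact).
- po = 18/38 = 0.474; pe = (10×10 + 28×28)/1444 = 884/1444 = 0.612.
- Kappa = (0.474 − 0.612)/0.388 = −0.36 (95% CI −0.50 to −0.21); positive agreement 0%.

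**Table 2: every anal infection is also cervical, (15, 7, 0, 16).**

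- McNemar = 7²/7 = 7.0; p = 0.008. With continuity correction, 6²/7 = 5.14 and p = 0.023. Exact p = 2 × (1/2)⁷ = 0.016.
- po = 31/38 = 0.816; pe = (22×15 + 16×23)/1444 = 698/1444 = 0.483.
- Kappa = (0.816 − 0.483)/0.517 = 0.64 (95% CI 0.42 to 0.87); positive agreement = 30/37 = 81%.

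**The extremes.** Total disagreement, (0, 19, 19, 0), has kappa −1 and p = 1. Perfect agreement, (19, 0, 0, 19), has kappa +1; with no discordant pairs the chi-square is 0/0 and the exact p is 1. The test cannot tell the two apart.

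**Rejection rates** (200,000 simulated samples of 38 women, nominal 5% level):

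| Assumed truth | Chi-square, uncorrected | Continuity-corrected | Exact |
|---|---|---|---|
| Independent sites, prevalence 50% at each (kappa 0) | about 5% | about 3% | about 3% |
| Type never shared, prevalence 25% at each | about 5% | about 3% | about 3% |
| Anal nested within cervical, 32% v 50% (kappa 0.64) | about 93% | about 70% | about 70% |

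The first two rows are McNemar's own null, so they simply return its error rate. That is the difficulty: absence of agreement, and even complete exclusion, is compatible with the hypothesis the test treats as no finding.

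**The case against.** The strongest reply has four parts.

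1. **The harm is not written into the plan.** Section 11.1 sets no threshold and does not say that a non-significant result means concordance. That is fair: the documents show that the result could be misread, not that it will be. But McNemar's test is the only method stated for the objective, and whichever way it is read it does not estimate agreement.

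2. **The tables are invented and favourable.** They are assumptions. Appendix XI lists 38 individual type-specific probes, and at the 5% reporting threshold a type would be present in about 2 of 38 women, so many real tables will be much sparser. The mismatch does not depend on the tables, because a and d are absent from the formula at any prevalence.

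3. **Kappa has its own problems when a type is rare.** At n = 38, (1, 1, 1, 35) gives kappa 0.47, with an approximate interval spanning zero. (0, 2, 2, 34) gives 89% overall agreement but kappa −0.06. This stands. It is why kappa should not be reported alone, and why the counts and positive agreement should carry the weight for rare types.

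4. **The stakes are limited.** The objective is exploratory, and the paired data will exist whatever the plan says, so agreement could be calculated later. McNemar's test is also a legitimate way to ask whether a type is found more often at one site. All of this stands and limits the importance of the point, but it does not make the test a measure of concordance.

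**Conclusion.** The concern holds. The only method named for objective 2.3.6.2 answers a different question, and nothing elsewhere in the plan supplies an agreement measure for HPV types or variants. Methylation in Appendix XI is also scored positive or negative per gene, so a difference in data type does not explain why one concordance analysis gets kappa and the other does not.

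The algebra needs no assumption. The sizes rest on the illustrative tables and on n = 38. The direction of the error is the same for the uncorrected, continuity-corrected and exact forms of the test; only the p-values and rejection rates move. The consequence is confined to this exploratory objective. The treatment completion analysis, the sample size and the safety assessment do not depend on it, and using McNemar's test for change from baseline to post-treatment is appropriate.

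**What to change.** Replace the concordance sentence in section 11.1 with wording such as: *For each HPV DNA type and strain variant, baseline cervical and anal results will be cross-classified within participant. The paired 2x2 counts, overall agreement, positive agreement and Cohen's kappa will be reported, each measure with a 95% confidence interval. For types found in few participants, the counts and positive agreement will be given precedence over kappa. McNemar's test may be added to compare prevalence between the two sites and will not be interpreted as a measure of concordance.*

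Leave the sentence on baseline to post-treatment change as it is. The cost is this one passage of wording. It needs no new specimens, visits or participants, and kappa is already among the planned methods.

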2.0 STUDY OBJECTIVES

2.1 Hypotheses

- 2.1.1 Treatment compliance will be comparable to what has been previously reported in retrospective studies (27).
- 2.1.2 The toxicity of weekly cisplatin in HIV-infected women on HAART is worse than that reported in HIV-uninfected women but manageable with limited dose reductions and dose delays.
 - 2.1.2.1 Recurrence patterns for HIV-associated LACC will be similar to that in HIV-uninfected women with LACC.
 - 2.1.2.2 Patients with poorly-controlled HIV (defined as CD4 count of $\leq 200/\mu\text{L}$ and/or HIV viral load ≥ 400 copies/mL) will have higher likelihood of distant recurrences.
- 2.1.3 The PFS at 1 year in HIV-infected women on ART who complete the prescribed cisplatin and RT doses of concomitant chemoradiotherapy with weekly cisplatin is similar, stage for stage, to the PFS in HIV-uninfected women stage for stage in LACC.
- 2.1.4 The subset of participants with poorly-controlled HIV as defined by baseline CD4 T-cell count and viral load will have worse PFS when compared with participants with well-controlled HIV infection.
- 2.1.5 Baseline measures of HPV types and strain variants, gene methylation patterns, and HPV serology and/or changes induced by therapy will be associated with the risk of subsequent recurrence of HIV-associated LACC.

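### Baseline methylation and HPV titer are tested against a yes/no persistence or recurrence with no time window and no rule for losses or deaths, although section 11.1 already uses time-to-event models for the change markers

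*Combined protocol and SAP*

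**What the plan says.** Section 11.1 of the combined protocol and SAP gives three relevant instructions.

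- Methylation: "The chi-square test will be used to assess the association between baseline gene methylation profiles and cervical persistence or recurrence".
- Titers: "The logistic regression model will be used to assess the effects of HPV-16 and HPV-18 serologic titer levels with disease persistence or recurrence", on log titer. The next sentence deals separately with change in titer, so I read this one as covering baseline titer, in line with objective 2.3.6.6.
- Change in HPV type: "Proportional hazards models and logistic regression models will be used to evaluate the association of change in DNA types with progression free survival and local" (the quote breaks off one word early; the second outcome is local control). Change in titer is handled the same way.

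Hypothesis 2.1.5 says that the baseline markers, or changes in them, "will be associated with the risk of subsequent recurrence of HIV-associated LACC". Section 9.2.1 defines PFS by the date of first recurrence, progression or death, so event dates are collected. Section 9.2.4 treats persistence as tumor status three months after therapy. On numbers, section 3.3 says "This study will enroll 45 participants, of whom we anticipate 38 will be evaluable", and section 11.2 says "To allow for potential 15% dropout, 45 patients will be enrolled in the study".

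**The concern.** A yes/no outcome has to be fixed at some time point, and every woman has to receive a value. Section 11.1 supplies neither rule for the baseline markers. A woman last seen at month 3 without disease could be coded as recurrence-free or left out. So could a woman who died without documented recurrence. Early and late failures also count alike.

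Two things are at stake. One is precision in an already small data set. The other is that the coding could be chosen after the data are seen. The Introduction expects these data to inform whether the markers are useful for persistence or recurrence, so the answer should not turn on an unstated choice.

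**Working it through.** **The plan's own figures.** The documents state no power, alpha, marker prevalence, recurrence rate or effect size for the marker tests, so there is no figure to reproduce for them. The enrolment figure does reproduce: 38/(1 − 0.15) = 44.7, so 45. (Separately, 38 evaluable for 0.50 against 0.70 with 0.90 power does not reproduce at the printed one-sided 0.0510. The normal approximation gives [(1.635 × 0.5 + 1.282 × 0.458)/0.2]² = 49.3. At one-sided 0.10 it gives 37.7, so 38. The sponsor should confirm the level. It does not enter this point.)

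**Inputs.** From the documents: N = 45 (38 evaluable), 15% dropout, 12 months of follow-up after treatment, visits every three months. Assumed: marker prevalence 30% to 50%, 12-month failure of 20% to 50% in marker-negative women, hazard ratio (HR) 2 to 3, two-sided 0.05, exponential failure times.

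**Step 1, formula, even marker split, no dropout.** Let p0 be the 12-month failure proportion in marker-negative women, p1 = 1 − (1 − p0)^HR, n = N/2 and D = n(p0 + p1).

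- Chi-square power = Φ{[(p1 − p0)√n − 1.96√(2p̄q̄)] / √(p0q0 + p1q1)}
- Log-rank power = Φ{√(D/4) × ln HR − 1.96}

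Example with p0 = 0.40, HR 2.5, N = 45: p1 = 0.721 and D = 25.2.

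- Chi-square: Φ{(0.321 × 4.743 − 1.96 × 0.702)/0.664} = Φ(0.22) = 0.588
- Log-rank: Φ{2.510 × 0.916 − 1.96} = Φ(0.34) = 0.633

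The gain is 4.6 points before rounding. Over p0 = 0.20 to 0.50 and HR 2 to 3, the gain runs from 1.4 to 6.8 points at N = 45 and from 1.3 to 8.1 at N = 38.

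**Step 2, simulation, N = 45, 15% dropout unrelated to the marker, failures detected at three-monthly visits.** Gains are taken before rounding.

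| Prevalence | p0 | HR | Log-rank | Chi-square, losses = no event | Chi-square, losses excluded | Gain, points |
|---|---|---|---|---|---|---|
| 50% | 0.30 | 2.0 | 0.280 | 0.268 | 0.277 | 1.2 / 0.3 |
| 50% | 0.30 | 2.5 | 0.488 | 0.468 | 0.480 | 2.1 / 0.9 |
| 50% | 0.40 | 2.5 | 0.579 | 0.524 | 0.559 | 5.5 / 2.0 |
| 50% | 0.50 | 2.5 | 0.673 | 0.563 | 0.608 | 11.0 / 6.6 |
| 30% | 0.30 | 2.5 | 0.456 | 0.406 | 0.416 | 5.0 / 4.0 |
| 30% | 0.50 | 2.5 | 0.626 | 0.496 | 0.509 | 13.1 / 11.7 |

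The top of the range at 15% dropout is 15.0 points (0.649 against 0.499: prevalence 30%, p0 = 0.50, HR 2.5, exact failure dates). With no true effect, type I error was 0.046 to 0.053 for all three tests.

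**Step 3, dropout that differs by marker.** Assumed: N = 45, 40% marker-positive, 40% failure at 12 months, three-monthly detection, no competing deaths, dropout 5% in marker-negative and 30% in marker-positive women. Overall dropout is still 0.6 × 5% + 0.4 × 30% = 15%.

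| True HR | Losses = no event | Losses excluded | Log-rank |
|---|---|---|---|
| 3 | 38% | 64% | 59% |
| 2.5 | 25% | 49% | 44% |
| 1 (type I error) | 7.7% | 5.6% | 4.9% |

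The codings differ by 64 − 38 = 26 and 49 − 25 = 24 points. A second simulation of the scenario gave 39% against 64% at HR 3, and type I error of about 6.5% for both codings against 5.0% for log-rank. Excluding losses showed more power than log-rank here, but it removes mainly event-free women, unequally by marker. With dropout of 10% and 50%, its type I error was 6.9% against 5.2% for log-rank.

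The simulations used a yes/no marker. Logistic regression on log titer was not simulated. The same coding gap applies to it, but the sizes above need not carry over.

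**The case against.** The strongest case for the plan is that its test matches its objectives. Objectives 2.3.6.5 and 2.3.6.6 ask about persistence or recurrence as such, and risk over a fixed window is legitimately binary. Follow-up is a fixed 12 months after treatment, which limits what time to failure can add. Persistence is a status with no onset date, and scheduled follow-up CT falls only at months 6 and 12, so failure times are coarse. Section 5.5 asks for an examination, and CT if the last is over three months old, at premature withdrawal where possible, so some women who leave will have disease status at exit. The analyses are exploratory and no power is claimed for them.

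Much of this stands. It rules out two stronger readings that a reader might infer.

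- *That the binary tests cost a definite amount, say 5 to 7 points of power.* Some settings give that, others give almost nothing or more than 10, and no input that would settle it is in the documents.
- *That the plan mishandles incomplete follow-up.* It is silent, which is different, and type I error held when dropout was unrelated to the marker.

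Nor is the 15% a forecast of lost disease follow-up. It inflates the sample for the treatment-completion endpoint. The Introduction reports considerable loss in an earlier trial but gives no number.

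What the objection does not answer is the missing window and coding, or why baseline and change markers are analyzed differently.

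**Conclusion.** The concern holds in a limited form. For baseline methylation and titer, section 11.1 sets aside failure times that are collected and leaves the yes/no outcome undefined for women lost early or dead without recurrence.

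With dropout up to 15% and unrelated to the marker, the power cost is roughly 0 to 15 points, typically a few, under assumed prevalence, failure rate and HR. If dropout differs by marker, the unstated coding matters more: about 25 points between the two codings in one scenario, with type I error of 5.6% to 7.7% for the binary tests against about 5% for log-rank. That advantage of log-rank rests on censoring that depends only on the marker. It would not cure dropout caused by unseen recurrence.

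Severity is minor. The tabled power in step 2 lies between 0.27 and 0.67 whichever test is used, and no primary objective depends on these analyses.

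**What to change.** In section 11.1:

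1. Add log-rank and proportional hazards analyses of PFS, as defined in section 9.2.1, for baseline methylation and baseline log titer, as the main test of association. This matches the change markers.
2. If time to persistence, progression or recurrence is also analyzed, date persistence at the three-month assessment and censor at the last disease assessment.
3. Keep the 2×2 and logistic analyses as supportive. State a 12-month window and how losses and deaths without recurrence are coded.

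This changes wording only, with no new data, visits or participants. The price is a proportional hazards assumption, which the section already accepts, and coarse visit-based failure times. PFS also counts deaths from any cause, so it answers a slightly different question from recurrence alone. Items 2 and 3 keep that question in view.
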